11. PARTICIPANT RIGHTS AND CONFIDENTIALITY	
12. COMMITTEES	39
13. PUBLICATION OF RESEARCH FINDINGS	39
14. REFERENCES	39
15. SUPPLEMENTS/APPENDICES	41
 Phone Pre-Screening of Inclusion/Exclusion Criteria Informed Consent Form for 14-17-year-old participants Informed Consent Form for 18-year-old participants Medical History Form Inclusion/Exclusion Criteria Form Enrollment/Randomization Form MRI Screening Form SDQ questionnaire Demographics questionnaire Baseline Checklist Form CORS CSRS On Study Visit Checklist Adverse Events Form 	
Serious Adverse Events Form	

• Study Completion Form

• TARA manual

• Protocol Deviation Tracking Log

STUDY TEAM ROSTER

[name],
Department of Radiology & Biomedical Imaging
University of California, San Francisco
[name]
[name]
[contact]

[contact] [contact]

[name], PhD, Department of Psychiatry, University of California, San Francisco [name] Langley Porter Psychiatric Institute [name] [contact]

[contact] [name]. [contact]

PARTICIPATING STUDY SITES

It is a single site study: please see the names and addresses above.

PRÉCIS

Study Title

Neural mechanisms of meditation training in healthy and depressed adolescents: An MRI connectome study

Objectives

The **primary objective** will be to study changes in putamen structural connectivity in healthy teens with meditation training. **Hypothesis**: Putamen structural node strength will increase in the training group compared to controls.

R61 Go/No-Go Criteria. Detect an effect size (a threshold of Cohen's d > 0.20) in changes of the primary mechanistic outcome (**Putamen structural node strength**) by the described meditation training in 100 healthy adolescents that are 14-18 years old and retain at least 80% of randomized participants for primary outcome measurement at the end of the study regardless of adherence to the intervention.

[figure not shown]
The **secondary objective** will be to study changes in emotional problems in healthy teens with meditation training. **Hypothesis**: There will be a significant decrease in emotional problems measured with the Strengths and Difficulties Questionnaire (SDQ) in the training group compared to controls.

Design and Outcomes

The current research study design will utilize an individually randomized group treatment, open-label, waitlist-controlled clinical trial to test the efficacy and safety of our innovative mindfulness meditation intervention (Training for Awareness Resilience and Action [TARA]) on the primary outcome (Putamen structural node strength) and secondary outcome (emotional problems measured with the Strengths and Difficulties Questionnaire [SDQ]) in healthy adolescents between the ages of 14 to 18 years old.

Please see below, Section 6.1 (Schedule of Evaluations), for detailed schedule and type of evaluations to be performed during the study.

R61 Overview Diagram of Study Design:

Interventions and Duration

The current study will specifically compare 12-week group meditation training intervention (TARA) with a waitlist control group. Each adolescent participant will be on study for the period of 12-weeks.

Sample Size and Population

The target population for the current study will be 100 healthy female and male adolescents that are between the ages of 14 to 18 years old who are randomly assigned to the 12-week meditation training intervention (TARA) or waitlist control group (50 healthy female and male adolescents between the ages of 14-18 years will be assigned to the 12-week meditation training intervention, and 50 healthy female and male adolescents between the ages of 14-18 years will be assigned to the waitlist control group). Randomization will not be stratified.

1. STUDY OBJECTIVES

1.1 Primary Objective

The **primary objective** will be to study changes in putamen structural connectivity in healthy teens with meditation training. **Hypothesis**: Putamen structural node strength will increase in the training group compared to controls.

R61 Go/No-Go Criteria. Detect an effect size (a threshold of Cohen's d > 0.20) in changes of the primary mechanistic outcome (**Putamen structural node strength**) by the described meditation training in 100 healthy adolescents that are 14-18 years old and retain at least 80% of randomized participants for primary outcome measurement at the end of the study regardless of adherence to the intervention.

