7.1 Specification of Safety Parameters

To demonstrate the safety of the TARA intervention, we will carefully record all adverse events and require that < 15% of the participants experience a grade 2 (moderate) or grade 3 (severe) adverse event related to the TARA intervention.

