9.4 Interim Analyses and Stopping Rules

This trial will not have any interim analyses. It is itself a preliminary study which will lead to a decision about whether a follow-on study will be conducted in depressed adolescent volunteers.

Safety findings that will trigger a safety review: If 15% of the enrolled study participants experience a Grade 2 (moderate) or Grade 3 (severe) adverse event (AE) related to the TARA study intervention, then a safety review will occur.

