9.5.2 Secondary Outcomes

The secondary outcomes include the following:

Emotional Problems. Emotional problems will be assessed by the SDQ questionnaire comparing the value before randomization (Visit 1) to the one 12 weeks

after randomization (Visit 14).

Other outcomes

Adherence. The proportion of volunteer randomized to TARA training who participate in at least 75% of the sessions. We expect that at least 80% of participants on the TARA arm will attain this level of adherence.

Safety and tolerability of the intervention. Adverse events will be collected at each visit and graded, and their attribution to their participation will be assessed. The safety of the TARA intervention will be demonstrated if < 15% of the participants experience a grade 2 (moderate) or grade 3 (severe) adverse event related to the TARA intervention.

To demonstrate the tolerability of the intervention used in this study, we will use the Child Session Rating Scale (CSRS) score. The CSRS is a 4-item self-assessments using a 10-cm visual analog scale (Campbell & Hemsley, 2011), with higher scores indicating better experience. This measure of tolerability will be completed after each session. Participants will rate the session in terms of how much they felt listened to, how important the content and activities were to them, how much they liked the session, and their overall experience. The intervention will be tolerable if the median CSRR is at least 20 in >80% of participants.

Retention. To demonstrate the ability to retain subjects, we will retain at least 80% of randomized participants for primary outcome measurement at the end of the study regardless of adherence to the intervention.

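### The R61 Go/No-Go criteria are not linked to the plan's own safety requirement of under 15%, so they can be met when that requirement has failed

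*Combined protocol and SAP*

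**What the plan says.** The Go/No-Go rule appears in the same words in the Précis and in Section 1.1. It has two parts: "R61 Go/No-Go Criteria. Detect an effect size (a threshold of Cohen's d > 0.20) in changes of the primary mechanistic outcome", which is putamen structural node strength, and to "retain at least 80% of randomized participants for primary outcome measurement at the end of the study regardless of adherence to the intervention".

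Section 9.4 gives the purpose of the trial: "It is itself a preliminary study which will lead to a decision about whether a follow-on study will be conducted in depressed adolescent volunteers".

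The safety limit stands elsewhere. Under Section 7.1 the investigators will "require that < 15% of the participants experience a grade 2 (moderate) or grade 3 (severe) adverse event related to the TARA intervention". Section 9.5.2 uses the same limit as a pass/fail test, under its other outcomes: "The safety of the TARA intervention will be demonstrated if < 15% of the participants experience a grade 2 (moderate" or severe) and related to TARA. Section 9.4 gives the one stated consequence of reaching the limit: "If 15% of the enrolled study participants experience a Grade 2 (moderate) or Grade 3 (severe) adverse event (AE) related to" TARA, "then a safety review will occur".

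No section says that missing the limit is a No-Go, or what the review may decide.

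**The concern.** Section 7.1 words the safety limit as a requirement, but the decision that the trial feeds does not depend on it. Section 9.5.2 lists retention and safety side by side, each with a numeric threshold. Retention was carried into the Go criteria and safety was not, and no reason is given.

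Two things are at stake. First, a report could state that the Go criteria were met and that safety was not demonstrated, with nothing in the plan to say which governs the move to depressed adolescents. Second, if that conflict is settled only after the data are known, the answer can be shaped by how good the imaging result looks.

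**Working it through.** **Inputs from the documents.** Design effect d = 0.6, two-sided alpha 0.05, power 80%, 45 evaluable subjects, 10% attrition, 50 per group (9.2). Go conditions: d > 0.20 and at least 80% retained (1.1). Safety limit: under 15% (7.1, 9.5.2). Allocation: 50 TARA, 50 waitlist (9.1).

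**The plan's own figure.** The normal approximation for two groups gives n = 2 × (1.96 + 0.84)² / 0.6² ≈ 43.6, so 44 per arm. The two-sample t-test gives 44.6, so 45 per arm, with power 0.804. Then 45 / 0.9 = 50. The stated size reproduces.

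**What the limit means in counts.** The denominator is not fixed: Sections 7.1 and 9.5.2 speak of the participants, 9.4 of enrolled participants.
- Denominator 50 (TARA arm): 7/50 = 14% passes and 8/50 = 16% fails.
- Denominator 100 (both arms): 14/100 passes and 15/100 = 15% fails. Waitlist participants have no TARA in the controlled period, so all 15 would have to come from the 50 in training.

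**Chance of meeting the two Go conditions at the design values.** With 45 per arm the standard error of the observed d is about √(2/45) = 0.211. P(observed d > 0.20 | d = 0.6) = 1 − Φ((0.20 − 0.60)/0.211) = 0.971. With true retention of 90%, P(at least 80 of 100 retained) = 0.999. Jointly, 0.971 × 0.999 = 0.970.

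**Chance that the safety requirement fails.** P(X ≥ k) = 1 − Σ C(50, x) pˣ (1 − p)⁵⁰⁻ˣ, summed over x = 0 to k − 1, with k = 8 or 15. The true rates p are assumptions. The two joint columns multiply by 0.970 and so also assume independence.

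| Assumed true rate | Fails, denominator 50 (k = 8) | Fails, denominator 100 (k = 15) | Go criteria met and safety failed, 50 | Same, 100 |
|---|---|---|---|---|
| 5% | 0.3% | <0.1% | 0.3% | <0.1% |
| 10% | 12.2% | <0.1% | 12% | <0.1% |
| 15% | 48.1% | 0.5% | 47% | 0.5% |
| 20% | 81.0% | 6.1% | 79% | 5.9% |

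**Whether the review catches the failures.** If one denominator applies throughout, failing the limit and triggering the review happen at the same count. If 7.1 is read on 50 and 9.4 on 100, then 8 to 14 affected TARA participants (16% to 28% of the arm) breach the requirement without a review. The chance of that is 48.1% − 0.5% = 47.6% at a true rate of 15%, and 81.0% − 6.1% = 74.9% at 20%.

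**The case against.** A reader might infer that safety has no part in the trial's conclusions, or that the protocol automatically sends an intervention that failed on safety into depressed adolescents. The documents support neither.
- Section 9.5.2 gives a pass/fail safety test, and 9.6 compares grade 2 or higher events between arms with the Fisher exact test. A failed limit would have to be reported as such.
- Under Table A the Independent Monitors see adverse event rates semi-annually and NCCIH sees them annually. Section 11.4 lets the IRB, NCCIH and other agencies discontinue the study.
- No section says that the two Go criteria are the only input to the follow-on decision. A safety gate could stand in the data and safety monitoring plan that 7.6 mentions, or in the later study's protocol; neither is among the documents.
- Sections 2.2 and 7.2 say that TARA was devised for adolescent depression and has been given to depressed adolescents, so the follow-on study would not be their first exposure.
- Adherence and tolerability thresholds are also outside the Go rule, which may reflect a deliberate separation. A fixed veto also replaces judgement.
- The large percentages need event rates of 15% to 20%, which nothing in the documents suggests, and a denominator of 50.

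All of this limits the point but does not remove it. The oversight powers are discretionary and the review has no stated outcome. Of the three thresholds left out of the Go rule, safety is the only one that the plan words as a requirement. A two-part rule printed under the primary objective will be read as the rule unless the protocol says otherwise.

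**Conclusion.** The concern holds as a missing link, not as a lack of safety evaluation. On the text alone, the written Go criteria can be satisfied after the Section 7.1 requirement has failed, and the only stated consequence is a review with no stated bearing on the follow-on study.

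The arithmetic only illustrates this. With 50 as denominator, the chance of failing the requirement runs from 0.3% at a true rate of 5% to 81% at 20%. With 100, it is about 0.5% at 15% and 6% at 20%. The joint figures also rest on d = 0.6, 45 scanned per arm, 90% retention and independence. If TARA is as low in risk as the plan says, the conflict will probably never arise. The denominator changes the answer so much that a safety condition could not be applied without fixing it.

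**What to change.** 1. In the Précis and Section 1.1, add that Go also needs the Section 7.1 safety requirement to be met.
2. In Section 9.4, state that the decision to "lead to a decision about whether a follow-on study will be conducted in depressed adolescent volunteers" needs all three conditions, and say how the safety review feeds into it.
3. In Sections 7.1, 9.4 and 9.5.2, use one denominator: participants assigned to TARA, because waitlist participants cannot have TARA-related events in the controlled period.

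The limit is the plan's own, so no new threshold and no new data are needed; the change is a sentence or two in each place. The downside is a slightly lower chance of Go. With 50 as denominator, the added condition would block 0.3% of trials at a true rate of 5% and 12% at 10%.

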1.2 Secondary Objectives

The **secondary objective** will be to study changes in emotional problems in healthy teens with meditation training. **Hypothesis**: There will be a significant decrease in emotional problems measured with the Strengths and Difficulties Questionnaire (SDQ) in the training group compared to controls.

2. BACKGROUND AND RATIONALE

2.1 Background on Condition, Disease, or Other Primary Study Focus

According to the World Health Organization (WHO), major depressive disorder (MDD) is the current leading cause of disability worldwide (Ferrari et al., 2013) and adolescence is an especially vulnerable period for the onset of depression. Depression has a prevalence by the end of adolescence of 20% (Brent & Birmaher, 2006) affecting the development of emotional, cognitive, and social skills which elevates the risk for suicide, substance use disorders, legal problems, physical illness, exposure to negative life events, early pregnancy, academic difficulties, family and friend problems, work problems, and poor psychosocial functioning (Birmaher et al., 2007; Essex et al., 2003; Infante et al., 2007). Depression during adolescence confers a 2- to 3-fold increased risk for adulthood depression (Pine et al., 1998). It is therefore of great importance both to develop prevention programs promoting emotional health and to intervene early with effective treatment of adolescent depression. Successful interventions during adolescence, when brain plasticity is peaking, may recover the aberrant neurocircuitry involved in emotional health.

2.2 Study Rationale

Non-pharmacologic approaches are particularly attractive due to the elevated risks of side effects related to the use of psychotropic drugs during development (Hetrick et al., 2007). Mindfulness meditation approaches are being explored for providing systematic training in emotional health (Vago & Silbersweig, 2012) and for treatment and prevention of depressive relapse (Kuyken et al., 2016). Our group has provided evidence that a meditative training (the same training we plan to use in our proposed study) can result in significantly strong effects of depressive symptom reduction in depressed adolescents (Henje [name] et al., 2016).

In the proposed study, we will use a type of **secular mindfulness meditation** practiced in the Training for Awareness, Resilience, and Action (TARA) (Henje [name] et al., 2014). The training was conceived in [name] (co-PI) lab at UCSF as a treatment program for adolescent depression. It is a semi-manualized 12-week group intervention, informed by mindfulness- and yoga-based techniques, and it takes into account developmental aspects of the adolescent brain that is still in the process of maturation (Henje [name] et al., 2014). TARA training includes several embodied mindfulness meditation practices (breathing techniques, yoga-based movements, and guided meditation), which are accompanied by short psycho-educational presentations and group discussions. A more detailed outline of the TARA training is presented in the "5.1 Interventions, Administration, and Duration" section below. The TARA program has shown excellent retention rates, positive participants' feedback, and improved functional outcomes (Henje [name] et al., 2016).

Scientific Rationale Behind the Hypothesized Primary Mechanism

In the center of our hypothesis is the node strength of the putamen, a region previously associated, on one hand, with the onset of meditation practice (Baerentsen et al., 2010) and attenuated shrinkage with age in Zen meditators (Pagnoni & Cekic, 2007), and on the other hand, with love, compassion, anticipation of pleasure and responses to increasing intensity of happiness (Bartels & Zeki, 2004; Klimecki et al., 2013; Surguladze et al., 2003). The graph theory measure of node strength (w) represents the sum of the edge weights connecting node i to all other nodes and highlights the centrality of the node within the network: $w_i = \sum_{j=1}^n a_{ij}$, where a_{ij} is the edge weight between nodes i and j, and n is the number of nodes. Importantly, it is not an isolated characteristic of a brain region but encompasses multiple white matter fiber projections connecting it, in the case of putamen, to motor, somatosensory cortices, limbic systems, and, to the largest degree, to frontal areas including the **prefrontal cortex** (Verstynen et al., 2012).

Here, we propose a **model** of how meditation training positively affects emotional health in healthy and depressed youth, where increase of the putamen's node strength is the hypothesized primary mechanism (Fig. 1). Our model is based on Garland Positive Reappraisal model and includes the neural mechanism, which links meditation practice to emotional health. Mindfulness meditation promotes non-evaluative and non-judgmental awareness in response to stimuli and even though increasing positive affect is

[figure not shown]

Figure 1. Proposed model of how meditation exerts its positive effects on emotional health in healthy and depressed adolescents. Based on Garland model of mindfulness and Davey model of adolescent depression.

not a goal per se in this type of meditation, the Positive Reappraisal theory suggests that mindfulness allows for a decentered mode of awareness from which new positive cognitive appraisals of self and world can be made (Garland et al., 2009) (Fig. 1). Primary appraisal of a stressor stimulus is usually followed by a cognitive process of secondary appraisal in which one's resources and coping options are weighted against the perceived demands of the situation.

Mindful decentering from this stress appraisal, wherein one attends to the dynamic process of consciousness itself rather than its contents, allows one to reappraise the event in a positive manner by attributing to it new meaning, in a way that engenders hope, resilience and creativity. The reappraisal then results in positive emotions such as compassion, trust, confidence, which in turn influence subsequent appraisal processes.

The role of putamen connectivity in meditation. We hypothesize that the transition from mindful decentering to positive emotion involves the fronto-striatal circuitry, specifically, the node strength of the putamen. The putamen has been implicated in both, onset of meditation practice (Baerentsen et al., 2010) and during continuous meditation by Lazar et al. (2000) and Tang et al. (2009), who reported increased activity in the putamen. Baerentsen et al. observed patterns of activations and deactivations in the brain, including pronounced activation in putamen with the onset of meditation practice. Remarkably, a 65% increase of endogenous dopamine release was observed in the striatum during meditation (Kjaer et al., 2002). We expect that regular engagement of the putamen will increase myelination of the white matter tracks connecting it to other regions (including the **prefrontal cortex**, PFC), which can be probed by using diffusion MRI fractional anisotropy (FA) indices as network weights. Our **preliminary results** in healthy adolescents using diffusion tensor imaging (DTI) and tractography (Fig. 2) show a medium-large effect of the putamen node strength increase during the meditation training compared to the waiting period and correlation of this increase with the self-reported amount of meditation practice. All specific statistics will be discussed in following sections.

The role of putamen connectivity in emotional health. The putamen's involvement in reward-related behavior and emotions has been well-studied (Lanciego et al., 2012). The basis of hedonic feelings has been studied through many different paradigms demonstrating association with striatal regions including the putamen (Gorwood, 2008). Increased functionality of the putamen is expected to decrease internalizing emotional problems such as feeling unhappy/worried/fearful and induce well-being and a more positive emotional tone. In alignment with this function of the putamen and its stimulation through meditation, our **preliminary results** in healthy adolescents show a decrease in emotional problems (internalizing subscale of the Strengths and Difficulties Questionnaire, SDQ) during the meditation training compared to the waiting period. We also observed in our **preliminary data** an association between the decrease in emotional problems and the increase of the putamen node strength, which provides support for the proposed model (Fig. 1).

[figure not shown]

Figure 2. From left to right: DTI-based whole-brain tractogram in a healthy adolescent (left image); the corresponding graph depicting the connectome with putamen nodes highlighted in red (middle image); tracks connecting the putamen with cortical regions in an adolescent brain (right image).

The role of putamen connectivity in adolescent depression. We also expect that meditation training will benefit adolescents suffering from depression by employing the described mechanism. Anhedonia – the decrease or loss of the ability to experience pleasure and happiness - is a key characteristic of major depressive disorder. Our **preliminary results** show that structural connectivity of the putamen is lower in depressed adolescents compared to healthy controls and that this hypoconnectivity is correlated with anhedonia, as we will show in more detail below. Gabbay et al. also reported abnormal resting-state functional connectivity of the putamen in depressed adolescents that significantly correlated with their levels of anhedonia (Gabbay et al., 2013). Since adolescence is a critical neurodevelopmental time period with significant remodeling and maturation of the dopaminergic reward system in the brain, Davey et al. have proposed a neurodevelopmental model that hypothesizes teen depression is due to the failure of the proper neurodevelopment of greater connectivity between the reward areas (i.e., putamen) and prefrontal cortical (PFC) areas (Davey et al., 2008). Their theory proposes that experiencing pleasurable and positive emotions is necessary for the proper neurodevelopment of the reward system during adolescence and that the lack of these experiences leads to the onset of adolescent depression. Mindfulness approaches are being explored for treatment and prevention of depressive relapse in adults (Kuyken et al., 2016). We have previously demonstrated that a meditative training (the training that will be used in this study) can result in a significantly strong effect of depressive symptom reduction in clinically depressed adolescents (Henje [name] et al., 2016). For these reasons, we chose to study meditation training for depressed adolescents as the optimization strategy for the R33 phase. As in the R61 phase, we expect increases in putamen node strength with practice of meditation. We expect that the mechanistic effect in the putamen will be amplified in the population of depressed as compared to healthy teens, which may reflect normalization of the putamen function. In our preliminary study of healthy adolescents, we observed a stronger increase of putamen node strength in those teens with lower baseline node strength. Our results in a small sample of adolescents with MDD show feasibility of recruitment and MRI scanning, and they also indicate a stronger increase of putamen node strength compared to healthy teens.

The proposed project will advance knowledge of the mechanism of action of meditation training by applying the most advanced neuroimaging approaches and by testing the proposed novel model (Fig. 1).

Biological and Psychological Relevance

The study population in the R61 phase will be healthy adolescents between the ages of 14-18 years. By this age, brain systems implicated in basic cognitive processes reach adult levels of maturity, whereas those that are active in the reward system are undergoing significant remodeling and neurodevelopmental maturation (Davey et al., 2008). The most rapid synaptic pruning is thought to occur between the ages of 12 and 16.5 years (Campbell et al., 2012), thus presenting an opportunity for long-lasting beneficial adaptations. In the R33 phase, we plan to study youth between the ages of 14-18 years who suffer from mild to moderate depression and who are under the care of a primary care doctor. During this critical time (14-18 years), the incidence of depression peaks and shows a dramatic, approximately three-fold increase (Hammen & Rudolph, 1996).

